### 8.5.2 Interim analyses and data monitoring

No interim analysis will be performed for this study.

## 8.5.3 Multiple comparison / multiplicity

Not applicable.

## 9. SAFETY EVALUATION

#### 9.1 Adverse events

The following safety/secondary endpoints will be descriptively summarized using the Safety set:

- Incidence of treatment failures (defined as haemostasis not achieved within 10 minutes or bleeding at the TBS during the ten-minute observational period that requires further hemostatic measures, other than re-application of the assigned hemostatic adjunct);
- Incidence of subjects with adverse events;
- Incidence of subjects with thrombotic events;
- Incidence of subjects with events associated with TBS re-bleeding;
- Proportion of subjects with no re-bleeding;
- Haemoglobin, Haematocrit, and Platelets, at screening, baseline, and post-surgery to hospital discharge (within 72 hours prior to discharge);
- Estimated intra-operative blood loss;
- Volume of blood and blood products transfusions (red blood cells, fresh frozen plasma, platelets, and cryoprecipitates), intra-operatively, prior to hospital discharge, and after discharge.

## 9.2 Clinical laboratory evaluation

Blood samples will be taken for full blood count with white blood cell differential, and coagulation parameters, at screening, baseline, and post-surgery to hospital discharge (within 72 hours prior to discharge).

## 9.3 Vital signs, physical findings and other observations related to safety

Vital signs will not be collected in this study. A physical exam will be performed and medical/surgical history data will be collected at screening. In addition, a physical exam will be performed post-surgery to hospital discharge (within 72 hours prior to discharge).

## 9.4 Methods of analysis

All safety/secondary variables will be summarized descriptively only, for Safety analysis set. No inferential statistical analysis will be carried out.

Page 8 of 18 Version: AMENDMENT 1 Date: July 1, 2019

Adverse events will be summarized descriptively by the treatment received, using Medical Dictionary for Regulatory Activities (MedDRA) terminology, in SI units. Values and changes from baseline will be listed, but not summarized.

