8 STATISTICAL METHODS

The Data Management and Biostatistics groups of Clinical Development, at Johnson & Johnson Global Surgery Group will be responsible for the overall analysis of data from this protocol. The detailed Statistical Analysis Plan (SAP) will be based on and will supplement the statistical design and analysis described in this section.

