8.4 Safety

8.4.1 Safety Variables / Criteria

The following will be summarised using the Safety Set:

- Incidence of treatment failures (defined as haemostasis not achieved within 10 minutes or bleeding at the TBS during the ten-minute observational period that requires further haemostatic measures other than re-application of the assigned haemostatic adjunct);
- Incidence of adverse events (including thrombotic events and events associated with TBS rebleeding).
- Proportion of subjects with no rebleeding;
- Laboratory and Blood Loss/Transfusion data will be summarised; and
- Clinically significant events will be recorded as AEs (Haemoglobin, Haematocrit, Platelets, Volume of blood loss; Volume of blood and blood products transfusion).

EudraCT Number: 2013-003401-26 Page 24 of 35

Amendment 4: 08 January 2018

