8.4.2 Methods of Analysis

Adverse events will be summarised descriptively by the treatment received, using Medical Dictionary for Regulatory Activities (MedDRA) terminology. Coagulation parameters (baseline and post-surgery samples) will use SI units.

Laboratory values (including coagulation parameters) will be reported in International System (SI) units. Values and changes from baseline will be listed and summarised. Clinically significant changes will be reported as part of the AE summary.

.

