#### 4. CHANGES IN THE CONDUCT OF THE STUDY OR PLANNED ANALYSIS

Not applicable.

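### SAP 9.4 rules out a summary of laboratory changes from baseline that protocol 8.4.2 requires, and does not declare the departure

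*SAP*

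**What the plan says.** Protocol 8.4.2 first deals with adverse events and then turns to the laboratory: "Laboratory values (including coagulation parameters) will be reported in International System (SI) units". The next sentence gives the rule: "Values and changes from baseline will be listed and summarised". Protocol 8.4.1 likewise lists for the Safety Set: "Laboratory and Blood Loss/Transfusion data will be summarised". The introduction to protocol Section 8 says that the SAP "will be based on and will supplement the statistical design and analysis described in this section".

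SAP 9.4 opens: "All safety/secondary variables will be summarized descriptively only, for Safety analysis set". Its second paragraph reads: "Adverse events will be summarized descriptively by the treatment received, using Medical Dictionary for Regulatory Activities (MedDRA) terminology, in SI units". It then closes: "Values and changes from baseline will be listed, but not summarized".

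SAP Section 4, on changes in conduct or planned analysis, reads in full: "Not applicable".

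**The concern.** The two closing sentences begin with the same words and give opposite instructions. If the SAP is followed, a descriptive safety summary that the protocol requires is dropped, and no reason is recorded.

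The variables affected include haemoglobin, haematocrit and platelets, which are named secondary endpoints in both documents. The trial has no formal sample size calculation and its safety analysis is descriptive only, so summaries of this kind are what the safety analysis delivers. A programmer also cannot follow every SAP instruction at once, because the closing sentence of 9.4 conflicts with the opening sentence of the same section.

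**Working it through.** The main check is a comparison of text. The plan gives no figure to reproduce.

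**1. Is the SAP sentence about laboratory data?** It does not say so; this is an inference. SAP 9.4 follows the order of protocol 8.4.2, but the laboratory sentence is missing. That leaves the reference to SI units attached to MedDRA-coded adverse events. Adverse events have no SI units, no values and no change from baseline, so the laboratory reading is the only one that makes sense.

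**2. Do the documents conflict?**

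| Item | Protocol | SAP |
|---|---|---|
| Laboratory values | Listed and summarised (8.4.2); summarised (8.4.1) | Not summarised (9.4, closing sentence); summarised (9.4 opening sentence, 8.4, 9.1, Tables 14.3.2.1 to 14.3.2.3) |
| Changes from baseline | Listed and summarised (8.4.2) | Listed, not summarised (9.4); named in no laboratory table or listing note in 10.2.2 or 10.3.1 |

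For values, the SAP contradicts itself as well as the protocol, and most of its text favours summarising. For changes, 9.4 is the only specific SAP instruction, and it is the reverse of the protocol's.

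**3. Is the departure declared?** No. Section 4 declares nothing. The change log at the front of the SAP covers only staged enrolment. That log compares SAP versions, so Section 4 is the stronger evidence.

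**4. Could the change summary be recovered from the time-point columns?** For paired values,

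Var(change) = SD1² + SD2² − 2·r·SD1·SD2.

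Assume SD1 = SD2 = SD. Then SD of change = SD × √(2(1 − r)), where r is the within-subject correlation. The documents give no r, so the range below is assumed.

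| r | √(2(1 − r)) | SD of change |
|---|---|---|
| 0.2 | √1.6 | 1.26 SD |
| 0.5 | √1.0 | 1.00 SD |
| 0.8 | √0.4 | 0.63 SD |

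The ratio of the extremes is 1.265 / 0.632 = 2.0. Over this range the same two columns fit a two-fold difference in the spread of change.

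**5. Which value is baseline?** The protocol (Schedule of Events footnote, 7.1.1 and 7.1.2) keeps the pre-operative result closest to surgery. SAP 9.1, SAP 9.2 and the laboratory tables name screening and baseline as separate time points and do not say which one a change is measured from. A subject whose retained sample came from screening may have no baseline-visit value. The baseline and post-surgery columns can then cover different subjects, and the difference between their means need not equal the mean paired change.

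**The case against.** The best reply is that this is a drafting slip with little consequence.

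- **Other SAP text favours summarising.** This stands for values. It does not settle changes: none of those places names a change from baseline, and the general opening sentence of 9.4 does not override the specific exclusion that closes it.
- **The table shells are in a separate attachment.** Shell L, used for all three laboratory tables, was not available for this review and may contain a change column. This stands, so the loss of the output is conditional on that shell. The conflict in the text is not.
- **The secondary endpoints are not defined as changes.** Correct. Haemoglobin, haematocrit and platelets are listed without reference to change, and SAP 9.1 specifies them by time point. The requirement to summarise change comes from protocol 8.4.2.
- **Individual changes would still be listed.** Correct under 9.4, and with a planned minimum of 40 subjects a reader could work from a listing. However, the laboratory listing notes mention no derived change, although other listings flag their derived data.
- **Clinically relevant shifts are captured elsewhere.** Partly. Protocol 8.4.2 sends clinically significant changes to the adverse-event summary, and Table 14.2.3 reports clinically significant changes since baseline. The first covers only changes judged clinically significant, and the second is not specific to laboratory data.
- **The correlation range is assumed.** It is. It only illustrates why time-point columns are not a substitute, and the conflict does not depend on it.
- **The protocol already settles baseline.** Largely so. The SAP still needs to say it, because its tables split screening from baseline.

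**Conclusion.** The concern holds, as a minor point. SAP 9.4 reverses protocol 8.4.2 on summarising laboratory changes from baseline, and SAP Section 4 does not declare it. This rests on reading the sentence as laboratory data, which is an inference but a secure one.

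The practical effect is limited. Values by time point should still be tabulated with counts of observed and missing results (SAP 10.2), and the primary endpoint is untouched. What would be lost, unless shell L already shows it, is the summary of within-subject change. Its spread cannot be read from the planned columns to better than a factor of two, given equal SDs and r between 0.2 and 0.8.

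**What to change.** In SAP 9.4:

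1. End the adverse-event sentence at the MedDRA reference and restore a separate sentence that reports laboratory values, including coagulation parameters, in SI units.
2. Replace the closing sentence with one stating that laboratory values and their changes from baseline are both listed and summarised descriptively by treatment received, on the Safety set.
3. Define baseline for the change as the single retained pre-operative result closest to surgery, whichever visit it came from.

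In Tables 14.3.2.1 to 14.3.2.3, add within-subject change, with the number of paired observations, if shell L does not already show it. A single pre-operative column would match the protocol's collection rule, but that is a suggestion only.

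If leaving out the summary is deliberate, record it with a reason in SAP Section 4 and bring 8.4, 9.1, 9.4 and 10.2.2 into line.

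The cost of the correction is one SAP paragraph and at most one shell that serves three tables. No new data are needed.

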## 10. DATA PRESENTATION

The report forms part of an integrated clinical study report. The actual numbering of tables, listings and other outputs may change. Numbering is in accordance with ICH guideline E3.

## 10.1 Procedure or treatment labels

The following labels will be used for all output: EVICEL and SURGICEL.

## 10.2 Tables and figures

Data will be tabulated by treatment group and, if appropriate, by visit. Continuous data summaries will present (unless stated otherwise) number of observations, number of missing observations (if there are any), mean, standard deviation, minimum, median and maximum. Categorical data summaries will present the number of observations and the corresponding percentage. The following tables will be produced:

## 10.2.1 In-text tables and figures

These will be produced for the main report in conjunction with the medical writer. These will include, but will not be limited to:

No	Title of table/figure	Notes
F1	Subject disposition	Based on Table 14.1.1.4
T1	Demographic characteristics – FAS analysis set	Summary of Table 14.1.2.1
T2	Surgical procedure – FAS analysis set	Summary of key items from Tables 14.1.3.1-14.1.3.9
Т3	Statistical summary for primary effectiveness endpoint – Per-Protocol and FAS analysis sets (including sensitivity analysis summary)	Summary of Tables 14.2.1.1 and 14.2.1.2
T4	Summary of AEs occurring in >5% of subjects— Safety analysis set	Summary of 14.3.1.3

T=Table F=Figure

## 10.2.2 Section 14 tables

Shell tables shown in Appendix 1, according to the code in the 'Shell' column. All table numbers will be prefixed with 14.

Page 9 of 18 Version: AMENDMENT 1 Date: July 1, 2019

No	Title of table/figure	Notes	Shell 
1.1	Disposition of subjects,		
	analysis sets and protocol		
1.1.1	deviations Disposition of subjects by	Includes number withdrawn – by center	DS
1.1.1	centre – FAS	includes number withdrawn – by center	DS
1.1.2	Enrollment by center – FAS	By center	Е
1.1.3	Summary of protocol deviations – FAS	Includes both minor and major protocol deviations	PD
1.1.4	Analysis sets – FAS		ST
1.2	Baseline data	Excludes baseline data that is also measured post procedure and/or safety data	
1.2.1	Demographics – FAS	Age, height, weight, BMI – continuous data (c); gender, race, ethnicity, and indication of subject being of child bearing age – all discrete data (d)	DG
1.2.2	Baseline characteristics – FAS	Presence of relevant history of prior surgery, indication of any relevant changes in medical history between screening and 24 hours before procedure, and confirmation of subject eligibility - all (d)	G1 
1.2.3	Physical exam / medical / surgical history – FAS	Includes frequencies	HX
1.3	Operative data		
1.3.1	Operative data: Surgery details and randomization – FAS	Primary operative procedure, primary method to obtain hemostasis at the TBS (prior to randomization), surgical approach, treatment to which subject is randomized (all d)	G2
1.3.2	Operative data: Target Bleeding Site (TBS) identification – FAS	TBS length (cm), width (cm), area (cm²) (all c), and location (d), type of bleeding (d), TBS tissue or parenchymal organ type (d), estimated intraoperative blood loss (mL) (c), indication of subject receiving blood or blood product transfusions from surgery through hospital discharge (d), indication of cell saver usage (d), and cell saver volume (mL) collected and returned (c)	G2
1.3.3	Operative data: EVICEL application – FAS	For patients treated with EVICEL: approximate amount of EVICEL used (up to 10 minutes following randomization) (mL) (c), total number of EVICEL kits used (both c and d), and quantity per kit (mL) (c)	G2
1.3.4	Operative data: SURGICEL application – FAS	For patients treated with SURGICEL: number of kits used (both c and d), indication of SURGICEL use according to IFU (d), approximated SURGICEL length and width (cm) used at the TBS (c), and SURGICEL area applied (cm  ) (c)	G2
1.3.5	Operative data: EVICEL application summary – FAS	For all EVICEL kits used: type of tip, method of application, and size of kit used (all d)	G2

<sup>1 Shell: Example table from Appendix 1 (Shell tables). Letters refer to standard output, numbers to project specific output.  For Tables G1, G2, G3 notes will indicate if data is continuous or discrete.

No	Title of table/figure	Notes	Shell 
1.3.6	Operative data: Hemostasis assessments – FAS	Time from randomization to initial application of randomized hemostatic product (sec) (c), TBS hemostasis presence at 4, 7, and 10 minutes from randomization (d), absolute time to hemostasis (from randomization) (sec) (c), and presence of any bleeding at TBS between 4 and 10 minutes following randomization (d)	G2
1.3.7	Operative data: Bleeding/durability details - FAS	Indication of any additional treatment use at the TBS (d) and indication of any rebleeding (d)	G2
1.3.8	Operative data: Treatments for re-bleeding – FAS	For all rebleeds - treatment used for re-bleeding (d)	G2
1.3.9	Operative data timings and other durations – FAS	Time in operating room (min), length of procedure (from first incision to last suture/staple) (min), length of procedure measured as time from first incision to initiation of fascial closure (when applicable) (min), time from screening visit to hospital admission (days), time from baseline visit to hospital admission (days), time from screening visit to surgery (days), and time from baseline visit to surgery (days) (all c)	G2
2	Effectiveness data		
2.1	Primary endpoint: Absolute time to hemostasis, elapsed from randomization	Includes analysis by age group; Includes 95% CIs for median absolute time to hemostasis, reported separately for EVICEL and control groups	
2.1.1	Primary effectiveness analysis: Absolute time to hemostasis, elapsed from randomization – FAS	Continuous data	G2
2.1.2	Primary effectiveness analysis: Absolute time to hemostasis, elapsed from randomization – PP set (confirmatory analysis)	Continuous data	G2
2.2	Secondary effectiveness endpoints		
2.2.1	Haemostasis at 4 minutes following randomization – FAS	Discrete data Includes 95% CI for proportion of subjects with hemostasis at 4 minutes separately for each group, as well as 95% CI for the ratio of proportions	G2
2.2.2	Haemostasis at 7 minutes following randomization – FAS	Discrete data Includes 95% CI for proportion of subjects with hemostasis at 7 minutes separately for each group, as well as 95% CI for the ratio of proportions	G2
2.2.3	Haemostasis at 10 minutes following randomization – FAS	Discrete data Includes 95% CI for proportion of subjects with hemostasis at 10 minutes separately for each group, as well as 95% CI for the ratio of proportions	G2

No	Title of table/figure	Notes	Shell 
2.2.4	Incidence of treatment failures (defined as haemostasis not achieved within 10 minutes or bleeding at the TBS during the ten-minute observational period that requires further hemostatic measures, other than reapplication of the assigned hemostatic adjunct) – FAS	Discrete data	G2
2.3	Follow-up assessments		G.S.
2.3	Post-surgery to hospital discharge (within 72 hours prior to discharge) and 30- day (±14 days) follow-up assessments – FAS	Indication of re-hospitalizations since hospital discharge (d), indication of surgical procedures since hospital discharge [both for 30-day (±14 days) visit only] (d), indication of relevant changes in medical history since screening (d), presence of clinically significant changes to subject since baseline (d), subject presence in elevated care unit (ICU, step-down unit, etc.) (d), duration of subject presence in elevated care unit (ICU, step-down unit, etc.) (c), subject presence on ventilator post-operatively (d), duration of subject being on ventilator post-operatively (c), length of subject hospital stay from admission to discharge (days) (c), and length of subject hospital stay from procedure to hospital discharge (days) (c)	G2
3	Safety data		
3.1	Adverse Events		
3.1.1	Number of subjects experiencing any during/post treatment AE by category – Safety analysis set		AS
3.1.2	Adverse events (during/post treatment) by subject, MedDRA preferred term and system organ class – Safety analysis set		AM
3.1.3	Summary of during/post treatment adverse events by subject and coded terms, preferred terms occurring in >=5% of subjects – Safety analysis set		AM
3.1.4	Summary of during/post treatment serious adverse events by subject and coded terms – Safety analysis set	Includes adverse events for which the answer for CRF question "Serious?" in the CRF is "Yes"	AM

No	Title of table/figure	Notes	Shell 
3.1.5	Summary of during/post treatment surgical procedure related (possibly, definitely) adverse events by subject and coded terms – Safety analysis set	Includes adverse events for which the answer for CRF item "Relationship to surgical procedure" is "Possibly related" or "Related".	AM
3.1.6	Summary of during/post treatment study treatment related (possibly, definitely) adverse events by patient and coded terms – Safety analysis set	Includes adverse events for which the answer for CRF item "Relationship to study treatment" is "Possibly related" or "Related".	AM
3.2	Laboratory data	Reported in SI units	
3.2.1	Laboratory data: Full Blood Count - Safety analysis set	At screening, at baseline, and post-surgery to hospital discharge - within 72 hours prior to discharge)	L
3.2.2	Laboratory data: White Blood Cell Differential - Safety analysis set	At screening, at baseline, and post-surgery to hospital discharge - within 72 hours prior to discharge)	L
3.2.3	Laboratory data: Coagulation Parameters - Safety analysis set	At screening, at baseline, and post-surgery to hospital discharge - within 72 hours prior to discharge)	L
3.3	Other safety data		
3.3	Safety/secondary endpoints  – Safety analysis set	Incidence of treatment failures (defined as haemostasis not achieved within 10 minutes or bleeding at the TBS during the ten-minute observational period that requires further hemostatic measures, other than re-application of the assigned hemostatic adjunct), incidence of subjects with thrombotic events, incidence of subjects with events associated with TBS re-bleeding, proportion of subjects with no re-bleeding (all d), estimated intra-operative blood loss (mL) (c), and volume of blood and blood products transfusions (red blood cells, fresh frozen plasma, platelets, and cryoprecipitates), intra-operatively, prior to hospital discharge, and after discharge (all c)	G2

Note: '-' indicates a new line in the title.

# 10.3 Listings

Listings will be presented in centre, subject and visit order. The listings will be produced using the data from all subjects.

The columns indicate the listings that will be included in the report. All data available on the database, with the exception of fields used for administration, e.g. signature fields, will be included in the listing for the report.

Missing data will be shown by a space.

# 10.3.1 Appendix 16.2 listings:

All listings will be prefixed with 16.2.

No	Title of listing	Notes	CRF Page
1	Disposition of subjects		
1.1	Disposition of subjects	Includes reason for withdrawal and time to withdrawal	55
1.2	Visit dates	Includes informed consent and discharge details	Various
		Includes derived data: -Nights in hospital -Days from procedure	
2	Protocol deviations	-Days from procedure	
2	Protocol deviations		51 and 53
3	Subjects excluded from the analysis		
3	Definition of analysis sets	As defined in Section 5 of this SAP	
4	Baseline characteristics		
4.1	Demographics, pregnancy test, and subject eligibility		1 and 6
4.2	Physical exam / medical / surgical history		8, 10, and 12
4.3	Inclusion and exclusion criteria		4
4.4	Concomitant medications	Derived data: -Days from procedure to start -Duration of Con Med	47 and 49
5	Surgical details		
5.1	Surgical procedure – timings, including operation room, procedure duration (from first incision to closure completion), procedure duration from first incision to initiation of final fascial closure, time from screening visit to hospital admission, time from baseline visit to hospital admission, time from screening visit to surgery, and time from baseline visit to surgery, and primary operative procedure	Includes derived data (timings)	1 and 14
5.2	Operative data - Target Bleeding Site (TBS) identification, blood and blood product use, hemostasis method, surgical approach, and randomization data		16 and 19
5.3	Operative data - EVICEL application		19
5.4	Operative data - SURGICEL application		19
5.5	Operative data - EVICEL application summary		19 and 20

No	Title of listing	Notes	CRF Page
5.6	Operative data - Hemostasis		23
	assessments		
5.7	Operative data -		25
	Bleeding/durability details		
5.8	Operative data - Treatments for		25
	re-bleeding		
6	Effectiveness data		
6.1	Effectiveness - primary		
	effectiveness endpoint		
6.1	Primary effectiveness endpoint -		
	absolute time to hemostasis,		
	elapsed from randomization -		
	FAS and PP set		
6.2	Effectiveness – secondary endpoints		
6.2	Secondary endpoints -		
	haemostasis at 4, 7, and 10		
	minutes following		
	randomization, and incidence of		
	treatment failures (defined as		
	haemostasis not achieved within		
	10 minutes or bleeding at the		
	TBS during the ten-minute		
	observational period that		
	requires further hemostatic		
	measures, other than reapplication of the assigned		
	hemostatic adjunct)		
6.3	Follow-up assessments		
6.3.1	Length of hospital stay	Includes derived data:	1
0.5.1	Dengan of nospital stay	-Days from admission to discharge	
		-Days from procedure to discharge	
6.3.2	Post-surgery to hospital		1, 27, 29, 35,
	discharge (within 72 hours prior		and 37
	to discharge) and 30-day (±14		
	days) follow-up assessments		
7	Safety data		
7.1	Adverse event listings (each		
	subject)		
7.1.1	Adverse events	Includes derived data:	41, 43 and 44
		-Days from procedure to start	
		-Duration of AE	1
7.1.2	Adverse event comments		43
7.1.3	Adverse events (MedDRA codes)		41, 43 and 44
7.1.4	Serious adverse events		41, 43 and 44
7.2	Laboratory data		
7.2.1	Laboratory data - Full Blood	At screening, at baseline, and post-	39
	Count	surgery to hospital discharge - within 72	
		hours prior to discharge)	
		 	•

No	Title of listing	Notes	CRF Page
7.2.2	Laboratory data - White Blood Cell Differential	At screening, at baseline, and post- surgery to hospital discharge - within 72 hours prior to discharge)	39
7.2.3	Laboratory data – Coagulation Parameters	At screening, at baseline, and post- surgery to hospital discharge - within 72 hours prior to discharge)	39
7.3	Other safety data		
7.3	Safety/secondary endpoints	Includes derived data: -Incidence of treatment failures (defined as haemostasis not achieved within 10 minutes or bleeding at the TBS during the ten-minute observational period that requires further hemostatic measures, other than re-application of the assigned hemostatic adjunct) -Incidence of subjects with thrombotic events -Incidence of subjects with events associated with TBS re-bleeding -Proportion of subjects with no re-bleeding -Estimated intra-operative blood loss -Volume of blood and blood products transfusions (red blood cells, fresh frozen plasma, platelets, and cryoprecipitates), intra-operatively, prior to hospital discharge, and after discharge	16, 19, 20, 23, 25, 31, 33, 43, and 44

